## 8. General Issues for Statistical Analysis

Descriptive summaries will be presented for each of the primary and secondary variables. In general, summaries will be completed for all patients overall and by age group as described in section 4.2.

Continuous, quantitative variable summaries will in general include the number of patients with non-missing values (N), mean, standard deviation, median, minimum and maximum, 1st and 3rd quartile.

Categorical, qualitative variable summaries will include the frequency and percentage of patients who are in the particular category. In general the denominator for the percentage calculation will be based upon the total number of patients in the analysis population unless otherwise specified.

Whenever appropriate, the analyses will be stratified according to the predefined age groups taken from the SCGAM-01 study (2 to <6 |  $\geq 6$  to <12 |  $\geq 12$  to <17 |  $\geq 17$  to  $\leq 75$ ).

Additionally, for primary and secondary endpoints, the following subgroups will be investigated:

- Male vs female subjects
- A different definition of age groups: 2 to < 12, 12 to < 17, 17 to 65, and > 65 years

### 8.1. Analysis Software

Statistical analyses will be performed using SAS Software version 9.1 or higher.

### 8.2. Withdrawals

Patients who withdraw from the study prematurely will be considered in all data presentations for which they contribute data; in particular for the analysis of annual rates they will be considered with their actual observation periods.

### 8.3. Handling of Missing Data

In general, missing data will not be imputed: calculations pertaining to person-year computations will be based on observed values only.

For missing weight measurements the last available body weight will be used for all calculations related to dosing; in individual patient data listings missing data will however not be replaced by imputed values.

No analyses of the patterns of missing data will be done.

For adverse events the following will be applied:

An Adverse Event (AE) is defined as treatment-emergent, if first onset or worsening is after start of the first infusion of *octanorm*.

If the start date and time of an AE are partially or completely missing, the AE will be assumed to be treatment-emergent if it cannot be definitely shown that the AE did not occur or worsen during the treatment emergent period (worst case approach). Missing dates and times will not be replaced.

For medications the following will be applied: A medication will be assumed to be concomitant if it cannot be definitely shown that the medication was not administered during the *octanorm* treatment period as defined in section 8.4 below. Missing dates will not be replaced.

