5.7.2 Assessment of Treatment Compliance

Patients will receive infusions at the study site and at home (administered at home by the patient or his/her relative or caregiver). Infusion details will be documented together with the batch number(s) in the eCRF.

Throughout the study, patients will be asked to document on a diary the date, batch (lot) numbers, number of vials, speed of infusion, injection site(s), occurrence of infections, TEAEs and local tissue reactions at injection sites, missed days from work/school/kindergarten/day care, inpatient hospital stays, and any changes in concomitant therapy between visits. The diary will be reviewed during the patient's infusion visit at the study site.

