- The **rate of infusions with one or more temporally associated AEs** will be calculated for each patient as  $r = (\text{Number of infusions with one or more temporally associated AEs}) / (\text{Number of infusions started})$ . An AE is defined as a temporally associated if, and only if, the onset (or worsening) is either during an infusion of study medication or within 72 hours of the end of the infusion. [Unit: N/A]
- The **rate of absence from work or school** will be based on the assumption of 200 working/school days per year, i.e. the rate is to be calculated as  $R = (1/200) \cdot (\text{Number of days absent from work or school}) / (\text{Patient years on octanorm treatment})$  [Unit: 1/years]

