### 11.1. Adverse Events

All reported AEs will be coded according to MedDRA.

An AE is defined as treatment-emergent, if first onset or worsening is during the *octanorm* treatment period. Only treatment-emergent AEs (TEAEs) are accounted for in the analysis.

For each TEAE, the time relative to the start of the infusion will be calculated and the TEAE will be classified as temporally associated if the onset is during the infusion or within 72 hours after the end of the infusion.

All reported events will be listed and tabulated in full detail, in particular the following key figures will be presented:

- Total number of TEAEs reported.
- Number of temporally associated TEAEs.
- Infusion rate at the onset of temporally associated TEAEs
- Narratives will be prepared describing each death, other SAEs, and other significant AEs that are judged to be of special interest because of clinical importance.

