### 11.2. Infusions with One or More Temporally Associated AEs

The number of infusions with at least one temporally associated adverse event (including AEs judged not to be related to *octanorm* by the investigator) over the total number of infusions will be calculated for each patient, and the ratio will be presented, including the associated upper one-sided 95% confidence limit. The calculation of this confidence interval will take into account the observed intra-patient correlation - this is necessary because each patient may experience more than one infusion with an associated AE; it can therefore not be assumed that the observed events are statistically independent.

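### The SAP gives no rule for temporal association when an AE onset is missing or partial; read literally, such AEs go uncounted, so the infusion-AE ratio can only fall or stay the same

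*SAP*

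**What the plan says.** SAP 8.3 expects that an AE start date and time may be partly or wholly absent. For treatment-emergence it takes the cautious side: "the AE will be assumed to be treatment-emergent if it cannot be definitely shown that the AE did not occur or worsen during" the treatment-emergent period. It then adds "Missing dates and times will not be replaced" and "No analyses of the patterns of missing data will be done".

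SAP 8.4 defines an AE as "temporally associated if, and only if, the onset (or worsening) is either during an infusion of study medication or within 72 hours" of the infusion's end. SAP 11.1 uses the same window: "the TEAE will be classified as temporally associated if the onset is during the infusion or within 72 hours after the end of the infusion". SAP 11.2 divides infusions with at least one such AE by all infusions, "including the associated upper one-sided 95% confidence limit". That limit is to allow for intra-patient correlation, but no formula is given for this ratio.

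None of these sections covers an onset that cannot be placed. Protocol 8.1.4 (missing data) and Protocol 9.2.3.1 (AE analysis) add nothing on it.

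On data capture, Protocol 5.7.2 asks patients to "document on a diary the date, batch (lot) numbers, number of vials, speed of infusion, injection site(s" and to note infections, AEs, local reactions and absences. It names no clock time. Protocol 8.1.1 lists the infusion details that must be verifiable from source, also without a clock time. SAP 9.4 does list infusion times among the items to be summarised.

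**The concern.** Temporally associated treatment-emergent AEs are one of the primary target variables (Protocol 3.1.1, SAP 3.2.1). The infusion ratio is the only result in SAP Section 11 with a planned confidence limit. The worst-case principle stops one step before this variable. An AE with an unplaceable onset is kept as treatment-emergent, but it cannot be shown to meet a strict two-way condition on timing.

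If the condition is programmed as written, the AE leaves the numerator while its infusion stays in the denominator. The error runs in one direction, the favourable one. With no review of missing-data patterns planned, a reader of the report would not see it.

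Incomplete times are plausible here. Most infusions are given at home, and AEs are collected at visits 12 weeks apart by an open question and diary review (Protocol 7.3.1.2).

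**Working it through.** The documents give no expected ratio, no expected share of missing times and no target limit, so there is no stated figure to reproduce. The shares and ratios below are assumptions.

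**Share of infusions at home.** Protocol 5.4 puts one infusion every 12 weeks on site. Weekly dosing: 1/12 = 8.3% on site, 11/12 = 91.7% at home. Bi-weekly dosing: 1/6 = 16.7% on site, 5/6 = 83.3% at home.

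**Which AEs are affected when the date is known.** Take an infusion of 1.5 hours (assumption). Share of each calendar day inside the window:

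| Infusion start | Day 0 | Day +1 | Day +2 | Day +3 | Day +4 |
|---|---|---|---|---|---|
| 09:00 | 0.625 | 1 | 1 | 0.438 | 0 |
| 14:00 | 0.417 | 1 | 1 | 0.646 | 0 |
| 19:00 | 0.208 | 1 | 1 | 0.854 | 0 |

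Days +1 and +2 lie wholly inside and day +4 wholly outside. Only the infusion day and day +3 need a clock time. If onset is uniform over the 72 hours after an infusion ending at hour h, these two days hold (24 − h)/72 + h/72 = 24/72 = one third of in-window AEs, whatever h is.

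**Effect on the ratio.** Let m be the share of affected infusions with an associated AE that cannot be placed. The reported ratio is at least r × (1 − m). It equals that only if no such infusion has another, placeable associated AE. If only the clock time is missing, replace m by m/3.

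| m (assumed) | r = 0.20, onset unplaceable | r = 0.20, only clock time missing |
|---|---|---|
| 5% | 0.19 | 0.20 × (1 − 0.017) = 0.197 |
| 10% | 0.18 | 0.20 × (1 − 0.033) = 0.193 |
| 20% | 0.16 | 0.20 × (1 − 0.067) = 0.187 |

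**Effect on the upper limit.** Two correlation-adjusted limits were tried by simulation: (a) the form in SAP 8.4, r × exp(1.645 × √(ΣCᵢ²/C²)), and (b) a linearised cluster ratio estimator. Settings were 35 patients with 100 or 234 infusions each and 45 patients with 100 each, true ratios of 5% to 20%, losses of 5% to 30%, and gamma between-patient variation with shape 0.7 (all assumptions apart from 35, 45 and 234). Results for 35 patients, 100 infusions each and a true ratio of 10%:

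| Loss | Ratio | Limit (a) | Limit (b) |
|---|---|---|---|
| none | 10.0% | 15.3% | 13.3% |
| 5% | 9.5% | 14.5% | 12.6% |
| 10% | 9.0% | 13.8% | 12.0% |
| 20% | 8.0% | 12.3% | 10.6% |
| 30% | 7.0% | 10.8% | 9.3% |

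The limit fell in every simulated setting under both methods, but it need not. Take two patients with 100 infusions each and 10 and 1 affected infusions. Form (a) gives 0.055 × exp(1.645 × √101/11) = 24.7%. Without the single event it gives 0.050 × exp(1.645 × 1) = 25.9%. The ratio falls and the limit rises.

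**The case against.** The strongest reply is that the documents are silent. A reader might infer that the SAP drops every AE without an onset time. No section says so. The definition in SAP 8.4 describes the event and is not written as a missing-data rule. SAP 8.4 also allows further derivations to be described in the study report if the SAP is not amended. This stands: exclusion is the literal reading, not a stated rule. But a derivation described only in the report is not pre-specified.

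Capture of times is clearly intended. SAP 9.4 lists infusion times without the restriction to centre visits that it puts on flow rates. SAP 11.1 calculates the time from infusion start for each event. Protocol 8.1.2 and 8.1.3 provide for queries until the data are clean. This may keep the number of affected AEs small. It does not say what happens to those that remain, and SAP 8.3 itself expects some.

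The study is descriptive (Protocol 9.2), and no decision in the documents rests on this limit. That lowers the stakes, but this is still a primary variable.

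Counting every unplaceable AE has its own bias. The 72 hours cover 72/168 = 43% of a weekly interval and 72/336 = 21% of a bi-weekly one. If onset were unrelated to infusion, more than half of the AEs with an unknown day would be wrongly counted. This stands, and is why the result must be shown both ways.

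**Conclusion.** The gap is real and worth closing, within limits. The worst-case rule covers treatment-emergence only, and nothing covers temporal association. Under the literal reading the ratio can only fall or stay the same.

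Two stronger conclusions are tempting and not supported. One is that the upper limit is always too low: it usually falls, but SAP 11.2 gives no formula, and under the SAP 8.4 form it can rise. The other is that the loss equals the share of AEs without a clock time. AEs dated on day +1 or +2 can be classified from the date alone, and the numerator counts infusions, not AEs.

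The size is unknown. With 5%, 10% or 20% of affected infusions carrying an unplaceable AE, the relative fall is at most 5%, 10% or 20%. If only clock times are missing it is about 1.7%, 3.3% or 6.7%. These figures rest on assumed missing shares and, for the second set, on uniform onset.

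**What to change.** Add to SAP 8.3 and 8.4: if the onset date or time of a treatment-emergent AE, or the infusion end time, is missing or partial, the AE counts as temporally associated with the most recent possible infusion, unless the available date parts show onset before that infusion or after calendar day +3.

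Report the number of AEs classified this way, separating those that lack only a clock time from those with an unknown day. The second group carries most of the risk of overcounting. Present the ratio and its upper limit with and without these AEs.

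The cost is a sentence or two in the SAP, a few lines of code and one extra run. The main ratio will be equal to or higher than under the literal reading, and it may overstate the true ratio; the paired presentation shows by how much the choice matters.

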### 8.4. Derived and Computed Variables

The following derived and computed variables have been initially identified as important for the analysis of the primary and secondary target variables. It is expected that additional variables will be

required. The SAP will not be amended for additional variables that are not related to the primary target or key secondary target variables. Any additional derived or computed variables will be identified and documented in the SAS programs that create the analysis files. If the SAP is not amended, further derivations related to primary and secondary target variables will be described in the CSR.

- **Age** will be derived according to the usual definition that a person is  $n$  years old until she or he has completed her or his  $(n+1)^{\text{th}}$  year of life, using the date of informed consent as the reference date. This is also the definition that will be applied for evaluation of the age related inclusion criteria, and the stratification into the four predefined age groups [Unit: years]
- **Body Mass Index:**  $\text{BMI} = (\text{Body weight}) / \text{Height}^2$  [Unit:  $\text{kg}/\text{m}^2$ ]
- The **octanorm treatment period** is defined as the period between the day of first treatment with study drug to the end of the observation period. This will usually be the termination visit.
- The **rate of serious bacterial infections** per year during regularly repeated treatment with *octanorm* will be calculated as  $r = (\text{Total number of serious bacterial infections occurring in the treatment period}) / (\text{Duration of treatment period})$  [Unit: 1/years]
- The **rate of other infections** will be derived using the same method

Calculation of the confidence intervals of these rates will account for intra-patient correlation in incidents following a compound Poisson process model.[1]

With  $C_i$  infections for the  $i^{\text{th}}$  patient, and  $C$  total infections, the adjusted 2-sided 98% CI is calculated by:

$$\left[ e^{\ln(r) - 2.33 \cdot \sqrt{\frac{\sum C_i^2}{C^2}}}; e^{\ln(r) + 2.33 \cdot \sqrt{\frac{\sum C_i^2}{C^2}}} \right]$$

- The **rate of infusions with one or more temporally associated AEs** will be calculated for each patient as  $r = (\text{Number of infusions with one or more temporally associated AEs}) / (\text{Number of infusions started})$ . An AE is defined as a temporally associated if, and only if, the onset (or worsening) is either during an infusion of study medication or within 72 hours of the end of the infusion. [Unit: N/A]
- The **rate of absence from work or school** will be based on the assumption of 200 working/school days per year, i.e. the rate is to be calculated as  $R = (1/200) \cdot (\text{Number of days absent from work or school}) / (\text{Patient years on octanorm treatment})$  [Unit: 1/years]

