All absences from work or school will be listed with duration and reason for absence. The individual absence rates per person-year will calculated and summarized by descriptive statistics, including the two-sided 90% confidence interval, again calculated on basis of the compound Poisson process model.

All hospitalizations will be listed with duration and indication for the inpatient hospital stay. The individual hospitalizations days per person-year will calculated and summarized by descriptive statistics, including the two-sided 90% confidence interval, again calculated on basis of the compound Poisson process model.

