## **14. Tables, Listings and Figures**

To be supplied in a separate document later when all feedback from authorities will be available.

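### Does the absence rate in SAP 8.4 carry the wrong unit, so that its values would mislead?

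*SAP*

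**What the plan says.** Missed days from work, school or day care is one of the secondary target variables in SAP 3.2.2. SAP 8.4 states that the rate of absence "will be based on the assumption of 200 working/school days per year, i.e. the rate is to be calculated as" R = (1/200) x (days absent) / (patient-years on treatment), and assigns it the unit 1/years.

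Two other derived rates in SAP 8.4 serve as comparators:

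- The serious bacterial infection (SBI) rate has as its numerator the "Total number of serious bacterial infections occurring in the treatment period", divided by the duration of that period. Its unit is 1/years.
- The rate of infusions with a temporally associated adverse event is a number of infusions divided by a number of infusions. Its bullet defines the time window as "within 72 hours of the end of the infusion. [Unit: N/A", so this ratio is marked as having no unit.

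SAP 10 covers reporting: "The individual absence rates per person-year will calculated and summarized by descriptive statistics", with a two-sided 90% confidence interval from the compound Poisson model. The next paragraph treats hospital stays similarly: "The individual hospitalizations days per person-year will calculated and summarized by descriptive statistics". No 1/200 factor is defined for hospital days. SAP 10 also promises that "All absences from work or school will be listed with duration and reason for absence". The table shells are not in the SAP; section 14 reads "To be supplied in a separate document later when all feedback from authorities will be available".

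**The concern.** The 200 is introduced as a number of days per year. Taken at its word, R is days divided by (days per year times years), which has no unit. It is the fraction of an assumed working or school year that was missed. A unit of 1/years and the phrase per person-year do not describe a fraction.

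The risk is a misreading of scale. SAP 10 places absence and hospitalization in consecutive paragraphs, both described per person-year. The hospital figure is in days, while the absence figure, if it is the R of SAP 8.4, is in two-hundredths of a day count. A reader who took an absence value of 0.05 for days per person-year would understate absence by a factor of 200. With the shells deferred, SAP 8.4 and SAP 10 hold the only unit and label that the SAP provides.

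**Working it through.** The SAP prints no numerical absence result, so the check is on the unit and on whether any value depends on how the unit is read.

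**Inputs.** From SAP 8.4: the divisor 200, the formula for R, its unit, and the units of the two comparator rates. From SAP 10: the 90% interval. The patient data below are assumed, for illustration only.

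**Step 1: unit under each reading of 200.**

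| Reading of 200 | Unit of R | R for 10 days in 1 patient-year |
|---|---|---|
| Days per year, as worded | none | 10 / (200 x 1) = 0.05 |
| Bare divisor, days as plain counts | 1/years | (10 / 200) / 1 = 0.05 |
| 200 days as one working year | 1/years (working years lost per patient-year) | (10 / 200) / 1 = 0.05 |

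The printed unit fails on the first reading and is correct on the other two. The value is the same on all three.

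**Step 2: which convention does SAP 8.4 follow?** Treating counts as dimensionless reproduces all three units:

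- SBI: count / years = 1/years, as printed.
- Infusions with an associated adverse event: count / count = no unit, as printed.
- Absence: count / 200 / years = 1/years, as printed.

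The no-unit entry for the infusion ratio therefore does not show that the absence entry is a mistake. That ratio has no time in its denominator, while the absence formula divides by patient-years.

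**Step 3: does a change of time unit settle it?** For 10 days absent in 12 patient-months:

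- If 200 is converted to 200 / 12 = 16.667 days per month, R = 10 / (16.667 x 12) = 0.05, unchanged, as for a unit-free share.
- If 200 stays a fixed divisor, R = 10 / (200 x 12) = 0.0042 per month. The annual value is 12 times that, as with an SBI rate of 1 per year, which becomes 1/12 = 0.083 per month.

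The result depends wholly on whether the 200 is converted, which is the point in question. The test cannot decide it.

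**Step 4: conversion to days.** Days per person-year = 200 x R. So 0.05 stands for 10 days and 0.02 for 4 days. With 45 days in 4.5 years, R = 45 / (200 x 4.5) = 0.05, again 10 days per person-year.

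**Step 5: confidence interval.** The SAP 8.4 interval has the form r x exp(-/+ z x s), with s = sqrt(sum of Ci^2) / C. For six assumed patients followed for 2 years each, with 10, 0, 4, 6, 0 and 20 days absent:

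- C = 40 and patient-years = 12, so the rate is 40 / 12 = 3.33 days per person-year.
- s = sqrt(100 + 16 + 36 + 400) / 40 = sqrt(552) / 40 = 0.587.
- With z = 1.645, the 90% interval is 1.27 to 8.76 days per person-year.
- With the factor 1/200, the rate is 0.0167 and the interval 0.0063 to 0.0438.

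Upper over lower limit is 6.9 in both cases. The constant moves the scale and leaves the relative precision as it was.

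**The case for a change.** The best case for a change is that the premise really is worded as days per year and is tied to the formula as its explanation. On that wording the result is a share, and the SAP has a way to mark unit-free quantities that it did not use here. Neither alternative reading of 200 is spelled out anywhere. Relabelling before the shells are finalised would cost one line and leave the derivation program alone.

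The literal reading is fair and probably describes what the sponsor wants to show, so the label could be clearer. That is all that stands. The printed unit has a consistent reading (step 2 of the check), and per person-year follows naturally from a denominator of patient-years. The misreading by 200 requires someone to overlook the definition in SAP 8.4. The shells are a separate document that may already carry a clear heading.

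A further point is that individual values can exceed 1 when follow-up is short, since for withdrawn patients "in particular for the analysis of annual rates they will be considered with their actual observation periods". With an assumed 5-day week, a patient absent on all 20 weekdays of a 28-day period (28 / 365.25 = 0.0767 years) has R = 20 / (200 x 0.0767) = 1.30. That is true, but it arises because 5 x 365.25 / 7 = 260.9 weekdays a year exceed the assumed 200. It bears on the 200-day assumption and says nothing about the unit. It also shows that renaming R a share would bring a difficulty of its own.

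**Conclusion.** The concern does not call for a change. The unit and label of one descriptive secondary variable can be read in more than one way, but the formula is explicit and gives the same value on every reading. On the likely intention, that absence is scaled to a 200-day year, no computed result is wrong. The derivation program, the relative width of the interval and the listing of absences with their durations are unaffected, and no safety or SBI result is touched. The factor of 200 is the size of a possible misreading of a table and is not an error in the analysis. An analyst writing the table heading would state what the figure counts as a matter of routine.

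This rests on two assumptions: that the absence rate in SAP 10 is the R defined in SAP 8.4, which is the only definition given, and that the 1/200 scaling is deliberate, as its wording indicates. Confidence that the printed unit is actually wrong is moderate at most. Confidence that nothing computed depends on it is high.
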